6.2 ACCESS TO BLINDED TREATMENT ASSIGNMENT

In the event of a medical emergency that requires immediate unblinding, an unblinding call may be made to determine treatment assignment. The identity of a subject's treatment assignment, should it need to be obtained, will occur through an unblinding call to the 24 hour [REDACTED]

[REDACTED]. Investigators will be permitted to access the treatment assignment upon the subject meeting the criterion for clinical worsening or after the completion of Day 14 if required for purposes of medically managing the subject (e.g., another prostacyclin will be initiated). Subjects randomized to placebo may be discontinued from study drug at that time. Subjects randomized to Remodulin who have residual or chronic pulmonary hypertension that does not fully resolve by Day 14 may continue to receive study drug for up to an additional 14 days (for a total of up to 28 days) per the Investigator's discretion. Subjects who have PPHN resolved by Day 14, who have already begun weaning by Day 14 or for whom it is anticipated that weaning of study drug will begin within

shortly after completing Day 14, or who are withdrawn from the study should remain blinded. All attempts should be made to maintain the blind during the study.

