9.1.5 Disease Related Events

PPHN is often associated with signs and symptoms of perinatal distress, including but not limited to, those listed in [Table 9-1](#). These events are anticipated to occur in the study population at some frequency independent of drug exposure. These events should be clearly documented in the subject medical record and identified as signs/symptoms of underlying disease under study.

Events that occur during the course of the study that are listed in Table 9-1 and felt to be related to the underlying disease under study by the Investigator will be recorded in the eCRF as disease related events. Events that are either serious or considered unusual with respect to intensity, frequency, or duration, or there is a reasonable possibility that it may have been caused by study drug as determined by the Investigator will also be recorded as an AE. All deaths, regardless of underlying cause, will be reported as an SAE.

Table 9-1 Expected Events Attributable to PPHN (System Organ Class and PREFERRED TERM, Ver. 17.0)

Hypoxia (Respiratory, thoracic & mediastinal disorders; HYPOXIA)	Pallor (Vascular disorders; PALLOR)
Cold extremities (General disorders and administration site conditions; PERIPHERAL COLDNESS)	Cyanosis (Cardiac disorders; CYANOSIS)
Cardiac arrhythmia (Cardiac disorders; ARRHYTHMIA)	Coagulopathy (Blood and lymphatic system disorders, COAGULOPATHY)
Tachypnea (Respiratory, thoracic & mediastinal disorders; TACHYPNOEA)	Respiratory distress (Respiratory, thoracic and mediastinal disorders; RESPIRATORY DISTRESS)
Polycythemia (Blood and lymphatic system disorders, POLYCYTHAEMIA)	Hyperviscosity syndrome (Blood and lymphatic system disorders, HYPERVISCOSITY SYNDROME)
Cardiovascular collapse (Vascular disorders; CIRCULATORY COLLAPSE)	Asphyxia (Respiratory, thoracic and mediastinal disorders; ASPHYXIA)
Postoperative hypotension (Vascular disorders, PROCEDURAL HYPOTENSION)	Tachycardia (Cardiac disorders; TACHYCARDIA)
Cor pulmonale (Cardiac disorders; COR PULMONALE)	Urine output decreased (Investigations, URINE OUTPUT DECREASED)
Weight loss (Investigations; WEIGHT DECREASED)	Shock (Vascular disorders; SHOCK)
Edema (General disorders and administration site conditions; OEDEMA)	Hepatomegaly (Hepatobiliary disorders; HEPATOMEGALY)
Respiratory failure (Respiratory, thoracic and mediastinal disorders; RESPIRATORY FAILURE)	

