15 APPENDICES

15.1 GUIDELINES AND DEFINITIONS FOR RECORDING ADVERSE EVENTS

For each adverse event, the Investigator will: (1) rate the intensity and seriousness of the AE, (2) estimate the causality of the AE to study drug, and (3) note actions taken to counteract the AE.

Definitions of Intensity, Seriousness, Causality, and Action Taken

Intensity

An assessment of the relative intensity (severity) of an AE is based on the investigator's clinical judgment. The maximum intensity encountered during the evaluation period should be checked. The assessment of intensity should be independent of the assessment of the seriousness of the AE.

- Mild: No limitation of usual activities.
- Moderate: Some limitation of usual activities.
- Severe: Inability to carry out usual activities.

Difference Between "Severe" and "Serious"

The term "severe" is often used to describe the intensity (severity) of a specific event (as in mild, moderate or severe myocardial infarction); the event itself; however, may be of relatively minor medical significance (such as severe headache). This is not the same as "serious", which is based on the outcome or action criteria usually associated with events that pose a threat to life or functioning. Seriousness (not severity) serves as a guide for defining regulatory reporting obligations.

Causality

An estimate of causality between a specified AE and the study drug is made by the Investigator.

Definitions of the categories follow:

- POSSIBLE - the AE MAY have been caused by study drug. There is a reasonable causal relationship between the study drug and the SAE. The event responds to dechallenge. Rechallenge is not required.
- PROBABLE - it is LIKELY that the AE was caused by study drug. There is a reasonable causal relationship between the study drug and the SAE. Dechallenge information is lacking or unclear.
- NOT RELATED - it is UNLIKELY that the AE was caused by study drug. There is not a temporal relationship to study drug administration (too early, or late, or study drug not

taken), or there is a reasonable causal relationship between another drug, or concurrent disease and the SAE.

Action Taken with Test Agent*

The action taken with test agent as a direct result of the AE:

- DOSE NOT CHANGED - there was no alteration in either the dose or regimen of the test agent
- DOSE INCREASED – dose was increased
- DOSE DECREASED – dose was decreased

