9.1 SUBJECT ACCOUNTABILITY

All subjects' disposition information will be listed, including the study population the subjects belong to, premature study drug discontinuation status, reason for premature study drug discontinuation, premature study discontinuation status, and primary reason for premature study discontinuation.

The listing of subject accountability will include dates of informed consent, randomization, first study drug dose, each study drug dose change, last study drug dose, and last assessment. Each of these assessments will be summarized by treatment group and overall.

Information regarding whether each subject is included in each analysis population will be listed. If a subject is not included in an analysis population, the reason for exclusion will be noted on the listing. Also noted on the listing will be the randomized treatment assignment and the actual treatment received. The summary will include the frequency and percentage of all subjects in each analysis population as well as summaries for reason for exclusion.

Status of the treatment blind and, if broken, date/time of blind broken and reason will be listed.

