12.2 ADVERSE EVENTS

All AEs will be coded to PT and SOC using the latest version of the MedDRA coding dictionary. Treatment-emergent adverse events (TEAEs) are those AEs with onset date equal to or after the start date of the study drug. TEAEs will appear in listings and summaries. Non-treatment-emergent AEs (the AEs occurring after signing the Informed Consent Form (ICF), but before receiving study drug) will be listed, but will not be included in summary tables.

The AE listings will include the AE verbatim term and its corresponding PT and SOC, all eCRF details, and a treatment-emergent indicator flag. The following AE listings will be provided:

- All AEs
- Deaths
- SAEs
- AEs leading to permanent discontinuation of study drug

All AE summaries will be sorted by overall frequency and/or SOC and will include the number and percentage of subjects experiencing each type of AE, the total number of each type of AE, and the AE rate of each type of AE. AE rate will be calculated as the total number of AEs divided by the total patient days of exposure to study drug per treatment group.

The following AE summaries will be provided:

- AEs by SOC and PT
- AEs by PT
- Deaths
- SAEs by SOC and PT
- Non-serious AEs by SOC and PT
- AEs probably or possibly related to study drug by SOC and PT
- AEs leading to permanent discontinuation by PT
- AEs by SOC, PT, and severity (mild, moderate, severe)

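### After a permitted code break the investigator may know the arm when rating relatedness, and the SAP pools those ratings with blinded ones, so the related-AE and disease-related tables are open to rater bias

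*SAP*

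**What the plan says.** **Who rates.** Protocol 15.1: "An estimate of causality between a specified AE and the study drug is made by the Investigator". Protocol 9.1.5 leaves a second decision to the same person. For the expected events of Table 9-1 the rule turns on the rater's opinion: those "felt to be related to the underlying disease under study by the Investigator will be recorded in the eCRF as disease related events". Such an event enters the AE data as well only if it is serious, is unusual in intensity, frequency or duration, or "may have been caused by study drug as determined by the Investigator will also be recorded as an AE".

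**When the rater may know the arm.** Protocol 6.2: "Investigators will be permitted to access the treatment assignment upon the subject meeting the criterion for clinical worsening or after the completion of Day 14". This is conditional on the infant's medical management requiring it. The same section asks sites to try to keep the blind, and keeps blinded those who at Day 14 have resolved, are weaning or are about to wean, and those withdrawn. Protocol 6.1.5 says ECMO alone is not a reason to unblind. The protocol does expect some placebo infants to be identified: Section 3.3.3 and a footnote to Table 3-1 waive the second PK sample and the weaning assessments for them.

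**What is tabulated.** SAP 12.2 counts every AE with onset on or after the start of study drug, with no cut-off at unblinding. Protocol 3.3.2.4 records AEs for up to four weeks after the last dose, unless discharge, death or withdrawal comes first. The related-AE summary ("AEs probably or possibly related to study drug by SOC and PT", Table 14.3.1.7) and the disease-related summary (SAP 12.4.3, Table 14.3.3) are by arm. On code breaks, SAP 9.1 says only: "Status of the treatment blind and, if broken, date/time of blind broken and reason will be listed".

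**The concern.** Relatedness is a judgement. A rater who knows that an infant is on placebo has little reason to call an event possibly or probably caused by the drug; one who knows that an infant is on Remodulin has reason to consider it. The same knowledge bears on whether a non-serious Table 9-1 event stays a disease-related event only or also becomes an AE.

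Two features make this more than a formality. First, the worsening route to unblinding is expected to open more often on placebo, because worsening is the primary endpoint and the design assumes a large difference in it. Second, Table 9-1 includes shock, circulatory collapse, procedural hypotension and coagulopathy, which overlap with the vasodilating and platelet-inhibiting actions described in Protocol 1.2 and the hypotension and bleeding cautions in Protocol 4.3.1. These are the events for which attribution is hardest and matters most.

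Safety is part of the primary objective. A by-arm table of related AEs will be read as a comparison even though Protocol 10.3.3 plans no tests.

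**Working it through.** **1. The plan's own figure.** The planning rates come from the sample-size sections (Protocol 10.2, SAP 5): 60% on placebo, 30% on Remodulin, one-sided 0.05, 80% power. Without continuity correction,

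n per arm = [1.645 × √(2 × 0.45 × 0.55) + 0.842 × √(0.60 × 0.40 + 0.30 × 0.70)]² / 0.30² = 32.9, so 33 per arm and 66 in total, with power 80.1%.

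The figure reproduces. It matters here only as the source of the two rates.

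**2. Infants for whom worsening could open the code.**

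- Placebo: 33 × 0.60 = 19.8.
- Remodulin: 33 × 0.30 = 9.9.

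On the planning rates, twice as many placebo infants reach the criterion. This is eligibility, not unblinding.

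**3. Why eligibility overstates exposure to the problem.** The composite includes death, after which there are no new AEs, and ECMO, which does not unblind by default. The 60% is anchored on 194/335 = 57.9% for death or ECMO alone. On that anchor 60 − 57.9 = 2.1 points, or 33 × 0.021 = 0.7 of an infant, would come from additional therapy alone. That is not a true split: an infant may start a vasodilator first and go on to ECMO or die later, and the documents give no breakdown. Unblinding after Day 14 adds infants by a separate route, again in unknown number.

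**4. Illustration for the percentage of infants with a related AE.** Every input except the 60% is assumed:

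- r: the share with a related AE if all ratings were blinded, equal in both arms;
- u: the share of worsened placebo infants who are unblinded;
- k: the share of those infants with a related AE who have it rated not related because the arm is known.

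Remodulin ratings are taken as unaffected, and the Day 14 route is ignored. False difference = r × 0.60 × u × k.

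| r | u = 0 | u = 0.25, k = 0.5 | u = 0.5, k = 0.5 | u = 0.5, k = 1 | u = 1, k = 1 |
|---|---|---|---|---|---|
| 30% | 0 | 2.25 points | 4.5 points | 9 points | 18 points |
| 50% | 0 | 3.75 points | 7.5 points | 15 points | 30 points |

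The last column is a ceiling, not a scenario: it needs every worsened placebo infant to survive, be unblinded, and have all related events rated after the break. The range starts at zero, and the documents do not say where in it the trial would fall.

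**5. The rate in the same tables.** SAP 12.2 divides the number of AEs by patient-days on study drug. Protocol 6.2 lets an unblinded placebo infant stop study drug, while AE recording continues. Let s be the share of placebo related AEs lost through knowledge of the arm, and d the share of placebo exposure-days lost through stopping. The placebo rate is multiplied by (1 − s)/(1 − d). It falls if s > d and rises if s < d. Neither is given, so the direction is unclear.

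**6. What is absent.** Neither document plans a blinded or independent review of causality, and no AE or disease-related summary is split or restricted by the code-break time.

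**The case against.** The case against is substantial:

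- **Unblinding is limited.** It needs a management reason, ECMO does not trigger it, and ratings made before the break are blinded unless revised later. This stands, and it is why the upper end of the illustration cannot be read as likely.
- **A known placebo infant can still have a related event.** Protocol 11.1 defines study drug as Remodulin or matching placebo, and the placebo contains metacresol and citrate and is infused, so an infusion-site event could properly be rated related. Protocol 15.1 also treats timing, including study drug not taken, as a ground for not related, so some late ratings of that kind in infants who have stopped would be correct. Both points weaken the mechanism without removing it.
- **Safety is descriptive, and all-cause tables exist.** All AEs, SAEs and deaths are already tabulated by arm. This answers much of the concern about relatedness. It does not fully answer the disease-related decision: a non-serious Table 9-1 event judged to be due to the disease alone stays out of the all-AE tables too.
- **The split can be made at reporting,** since onset date and time (Protocol 9.2) and code-break time are captured. True, but a supportive analysis is worth more when specified beforehand.

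A reader might infer that the related-AE table is biased, and by a calculable multiple. The documents do not support that. They show that the rater may know the arm, but give neither an unblinding fraction nor a measure of how ratings would shift.

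**Conclusion.** The point holds as an exposure to bias. After a permitted code break the person who rates causality and classifies Table 9-1 events may know the arm, and SAP 12.2 and 12.4.3 pool those ratings with blinded ones. Table 14.3.1.7 (counts and percentages) and the disease-related/AE split behind Table 14.3.3 are therefore open to rater bias. The probable direction is fewer related events on placebo, on the assumptions that raters are less inclined to blame a drug they know was not given and that more placebo infants reach the worsening criterion, as the design expects. For the rate per exposure-day the direction is unclear.

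No size can be given. The primary efficacy analysis, sample size and power are untouched. This is a cheap improvement rather than a defect that undermines the trial.

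**What to change.** In SAP 12.2 and 12.4.3:

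1. Use the recorded date and time of any code break, emergency unblinding included, to flag each AE and disease-related event as starting before or after it. If the date of the causality rating is captured, flag by that as well.
2. Keep Tables 14.3.1.7 and 14.3.3 as planned and add supportive versions split by the flag. For the before-break part use blinded patient-days as the denominator. Note beside it that this part ends at an outcome-driven time that may differ by arm, so it supports the full tables and does not replace them.
3. State that the between-arm safety comparison rests on all-cause AEs, SAEs and deaths.
4. Add one by-arm table of every Table 9-1 event over the whole observation period, whether recorded as disease-related, as an AE or both, counting each event once. Attribution then cannot decide what is counted. Table 9-1 uses MedDRA 17.0 terms and SAP 12.2 codes to the latest version, so the term match should be specified.

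A tempting alternative is to record all Table 9-1 events as AEs once the code is broken. It should not be adopted: breaks are likelier on placebo, so it would add AEs selectively to that arm and distort the all-cause comparison in item 3.

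The cost is one flag derived from data already captured, a few extra tables, and fewer events in the before-break comparison.

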12.3 CLINICAL LABORATORY EVALUATIONS

Blood samples will be taken at Baseline, Day 7, Day 14, immediately prior to study drug weaning or discontinuation, within 12 hours of study drug discontinuation, 48 hours after study drug discontinuation, and upon hospital discharge or 4 weeks after study drug discontinuation. All samples will be sent to the institutional laboratory for evaluation of clinical chemistry and hematology.

12.3.1 Clinical Chemistry

The following clinical chemistry parameters will be evaluated by the central laboratory:

Parameter	Units
Sodium	mmol/L
Potassium	mmol/L
Bicarbonate	mmol/L
Chloride	mmol/L
Total bilirubin	umol/dL
Alkaline phosphatase	U/L
Alanine aminotransferase	U/L
Aspartate aminotransferase	U/L
Urea nitrogen	mmol/dL
Creatinine	umol/L
Glucose	mmol/L
Calcium	mmol/L
Albumin	g/L
Lactate	mg/dL
pH	

Values that are “high” or “low” with respect to the reference range provided by the central laboratory will be flagged with an “H” or an “L,” respectively. All parameters will be listed for all subjects and assessments, along with their respective “high/low” flags.

Values of these parameters at each scheduled timepoint and their corresponding changes from Baseline will be descriptively summarized.

For each parameter, the frequency and percentage of subjects within each treatment group who had “low,” “normal,” or “high” Baseline values, then subsequently had “low,” “normal,” or

“high” follow-up values at each scheduled timepoint will be presented in a shift summary at each scheduled timepoint.

12.3.2 Hematology

The following hematology parameters will be evaluated by the central laboratory:

Parameter	Units
Hemoglobin	g/dL
Hematocrit	%
Red blood cell count	10 ⁶ /uL
White blood cell count	10 ³ /uL
Platelet count	10 ³ /uL
Prothrombin time	sec

Values that are “high” or “low” with respect to the reference range provided by the central laboratory will be flagged with an “H” or an “L,” respectively. All parameters will be listed for all subjects and assessments, along with their respective “high/low” flags.

Numeric values of these parameters at each scheduled timepoint and their corresponding changes from Baseline will be summarized.

For each parameter, the frequency and percentage of subjects within each treatment group who have “low,” “normal,” or “high” Baseline values, then subsequently have “low,” “normal,” or “high” follow-up values at each scheduled timepoint will be presented in a shift summary.

12.4 OTHER SAFETY MEASURES

12.4.1 Echocardiograms

Echocardiograms will be collected at Screening, Day 7, Day 14, immediately prior to study drug weaning or discontinuation, and 48 hours after study drug discontinuation. All echocardiogram assessments will be listed for all subjects. This listing will include the date and time of assessment, tricuspid regurgitant jet velocity, pulmonary regurgitant jet velocity, shunting details (through patent ductus arteriosus, through atrial septal defect or patent foramen ovale, and through ventricular septal defect), right ventricle dilation, and interventricular septal position.

The echocardiogram results will be descriptively summarized by treatment group at each planned assessment time.

12.4.2 Vital Signs

All vital sign assessments will be listed for all subjects. This listing will include weight, length, heart rate, systolic and diastolic blood pressures, respiration rate, temperature, and SpO₂. The vital sign results at each scheduled timepoint and the associated change from Baseline will be descriptively summarized by treatment group.

12.4.3 PPHN Disease-related Events

The number and percentage of subjects who experienced any PPHN disease-related event will be summarized by treatment group. Each category of disease-related event will also be summarized by treatment group. A listing of PPHN disease-related events will also be provided.

13 PHARMACOKINETICS

A listing that includes treprostinil plasma concentration, sample collection date and time, and nominal timepoint will be created. A separate listing will include the calculated PK parameters (if possible) for each subject.

Treprostinil plasma concentrations and PK parameters will be summarized by treatment group and nominal timepoint. The summary will include geometric mean and standard deviation in addition to arithmetic mean, standard deviation, minimum, and maximum.

Full details for the analysis of the PK data will be provided in a separate analysis plan.

15 LIST OF TABLES, LISTINGS, AND FIGURES

15.1 LIST OF TABLES

Table Number	Table Title
14.1.1	Summary of Subject Accountability
14.1.2	Summary of Analysis Population Information
14.1.3	Summary of Demographic Data
14.1.4	Summary of Baseline Characteristics
14.1.5	Summary of PPHN History
14.1.6	Summary of Neonatal History
14.1.7.1	Summary of Entry Criteria Violations
14.1.7.2	Summary of Protocol Deviations
14.1.8	Summary of Medical History
14.1.9	Summary of Concomitant Medications Ongoing at Baseline
14.1.10	Summary of Concomitant Medications Added During the Study
14.1.11	Summary of Study Drug Dosing and Exposure
14.2.1.1	Summary and Analysis of Clinical Worsening through Day 14 – Primary Efficacy Endpoint – ITT Population
14.2.1.2	Summary and Analysis of Clinical Worsening through Day 14 – Primary Efficacy Endpoint – Per Protocol Population
14.2.2.1	Summary and Analysis of Oxygenation Index – Secondary Efficacy Endpoint
14.2.2.2	Summary and Analysis of PaO ₂ /FiO ₂ – Secondary Efficacy Endpoint
14.2.2.3	Summary and Analysis of Pre-ductal SpO ₂ – Secondary Efficacy Endpoint
14.2.2.4	Summary and Analysis of Post-ductal SpO ₂ – Secondary Efficacy Endpoint
14.2.2.5	Summary and Analysis of NT-proBNP (pg/mL) – Secondary Efficacy Endpoint
14.2.2.6	Summary and Analysis of Time to Clinical Worsening – Secondary Efficacy Endpoint
14.2.2.7	Summary and Analysis of Time to Initiation of ECMO – Secondary Efficacy Endpoint
14.2.2.8	Summary and Analysis of Time to Discontinuation of iNO – Secondary Efficacy Endpoint
14.2.2.9	Summary and Analysis of Time on Mechanical Ventilation – Secondary Efficacy Endpoint
14.3.1.1	Overall Summary of Adverse Events
14.3.1.2	Summary of Adverse Events by System Organ Class and Preferred Term
14.3.1.3	Summary of Adverse Events by Preferred Term
14.3.1.4	Summary of Deaths
14.3.1.5	Summary of Serious Adverse Events by System Organ Class and Preferred Term
14.3.1.6	Summary of Non-serious Adverse Events by System Organ Class and Preferred Term

Table Number	Table Title
14.3.1.7	Summary of Adverse Events Probably or Possibly Related to Study Drug by System Organ Class and Preferred Term
14.3.1.8	Summary of Adverse Events Leading to Permanent Discontinuation of Study Drug by Preferred Term
14.3.1.9	Summary of Adverse Events by System Organ Class, Preferred Term, and Severity
14.3.2.1	Listing of Deaths
14.3.2.2	Listing of Serious Adverse Events
14.3.3	Summary of PPHN Disease Related Events
14.3.4.1	Summary of Laboratory Data – Clinical Chemistry
14.3.4.2	Summary of Clinical Chemistry Shift from Baseline
14.3.4.3	Summary of Laboratory Data - Hematology
14.3.4.4	Summary of Hematology Shift from Baseline
14.3.5	Summary of Vital Signs
14.3.6	Summary of Echocardiogram Parameters
14.3.7.1	Summary of FiO ₂
14.3.7.2	Summary of Blood Gas
14.3.7.3	Summary of Lactate
14.4.1	Summary of Plasma Treprostinil Concentrations
14.4.2	Summary of Pharmacokinetic Parameters

